# 3.12 Subject Compliance

Responsible trial personnel will dispense the IMP (ie, brexpiprazole, aripiprazole, and placebo) to subjects. Accountability and compliance verification should be documented in the subject's trial records. Subjects must be counseled on the importance of taking the IMP as directed at all trial visits. If poor compliance continues after counseling (eg, multiple missed doses resulting in less than 80% overall compliance), discontinuation of the subject from the trial should be considered.

# 3.13 Protocol Deviations

This trial is intended to be conducted as described in this protocol. In the event of a significant deviation from the protocol due to an emergency, accident, or mistake (eg, violation of informed consent process, IMP dispensing or subject dosing error, treatment assignment error, subject enrolled in violation of eligibility criteria or concomitant medication criteria), the investigator or designee will contact the sponsor at the earliest possible time by telephone. The investigator and sponsor will come as quickly as

possible to a joint decision regarding the subject's continuation in the trial. This decision will be documented by the investigator and the sponsor and reviewed by the site monitor.

# 4 Restrictions

# 4.1 Prohibited Medications

All subjects must agree to discontinue all prohibited medications during the screening period in order to meet the protocol-specified washout periods. Table 4.1-1 provides the required duration of washout for selected prohibited medications. All other prohibited medications must be discontinued at least 24 hours before the first dose of double-blind IMP. Other therapies prohibited prior to enrollment and during the trial are presented in Section 4.2. The Medical Advisor must approve the use of all supplements, vitamins, and over-the-counter medications with the exception of episodic use of ibuprofen, acetaminophen/paracetamol, naproxen, or equivalent.

| Table 4.1-1         Washout of Prohibited Medications Required          |  |  |  |  |  |
|---|--|--|--|--|--|
| Before the Trial  |  |  |  |  |  |
| Medication  | Required Washout Prior to Dosing             |  |  |  |  |
| Antipsychotics  |  |  |  |  |  |
| Oral aripiprazole   | 14 days                                      |  |  |  |  |
| Oral antipsychotics (other than cariprazine and clozapine)              | 7 days                                       |  |  |  |  |
| Depot or long-acting injectable antipsychotics                          | $5 \times$ half-life of the medication prior |  |  |  |  |
|   | to screening                                 |  |  |  |  |
| Cariprazine (Vraylar) and clozapine                                     | 6 months                                     |  |  |  |  |
| Antidepressants   |  |  |  |  |  |
| Fluoxetine or Symbyax   | 28 days a                         |  |  |  |  |
| MAOIs   | 14 days                                      |  |  |  |  |
| Citalopram and escitalopram   | 8 days                                       |  |  |  |  |
| Venlafaxine and desvenlafaxine  | 3 days                                       |  |  |  |  |
| All other antidepressants   | 14 days                                      |  |  |  |  |
| Atomoxetine   | 28 days with the diagnosis of                |  |  |  |  |
| Stimulants  | ADHD; minimum 5× half- life for              |  |  |  |  |
| Stinuants   | subjects without diagnosis of ADHD           |  |  |  |  |
| Mood stabilizers (ie, lithium or anticonvulsants)                       | 7 days                                       |  |  |  |  |
| Varenicline   | 5 days                                       |  |  |  |  |
| Oral benzodiazepines used as rescue therapy during washout b |  |  |  |  |  |
| Lorazepam, oxazepam, diazepam, or clonazepam                            | 12 hours before scales c          |  |  |  |  |
| Other benzodiazepines   | 14 days                                      |  |  |  |  |
| CVD2D6 inhibitors and CVD2A4 inhibitors and inducers                    | 14 days                                      |  |  |  |  |
| (see Table 4.1-4)   | 14 uays                                      |  |  |  |  |
|   |  |  |  |  |  |

MAOIs = monoamine oxidase inhibitors.

aIf extension to the screening window is needed for washout, contact the medical director.

bUse of IM benzodiazepines and continual use of oral benzodiazepines are prohibited throughout the trial. However, limited use of specific oral benzodiazepines is permitted during screening to treat agitation or insomnia (see Table 4.1-3).

cBenzodiazepines must not be administered within 12 hours prior to scheduled efficacy and safety assessments, including EPS scales. Investigators are encouraged to delay scale administration until 12 hours have elapsed, if at all possible. However, if delaying administration of efficacy and safety scales is not feasible, the scales should still be administered and the use of benzodiazepine documented, including a notation of the drug name, dose, and time of administration in eSource.

Table 4.1-2 lists all medications prohibited during the trial, including exceptions, where appropriate.

| Tabl | e 4.1-2 List of Medications Prohibited During the Trial  |
|------|--|
| 1.   | 
 
All psychotropic agents including, but not limited to, the following:
 
a) Antipsychotics, including IR IM and depot or long-acting injectable formulations
 
b) Antidepressants (including MAOIs)
 
c) Symbyax
 
d) Moderate illegram (including management)
 
                                    |
|      | 
 
e) Benzodiazepines, except specific benzodiazepines when used as rescue therapya
 
f) Stimulants with the diagnosis of ADHD and treatment with stimulants within 28 days, otherwise washout of > 5× half- life for subjects without diagnosis of ADHD
 
g) Other psychotropics (ie, atomoxetine)
 
 |
| 2.   | Ramelteon and other non-benzodiazepine sleep aids, except for limited use of specific medications for the treatment of insomnia b   |
| 3.   | Antihistamines (except for loratadine and cetirizine)  |
| 4.   | Varenicline  |
| 5.   | Other nutritional supplements and nonprescription herbal preparations with central nervous system effects (eg, , St. John's Wort, omega-3 fatty acids, kava extracts, GABA supplements ) unless approved in advance by the medical monitor   |
| 6.   | CYP2D6 inhibitors and CYP3A4 inhibitors and inducers (see Table 4.1-4)   |
| 7.   | Investigational agents   |

GABA = gamma-aminobutyric acid; IR = immediate-release.

aUse of IM benzodiazepines and continual use of oral benzodiazepines are prohibited throughout the trial. However, limited use of specific oral benzodiazepines is allowed for the control of agitation or insomnia as shown in Table 4.1-3.

bNon-benzodiazepine sleep aids (ie, zolpidem, zaleplon, zopiclone, and eszopiclone only) are permitted for the treatment of insomnia, but not on the same day as administration of a benzodiazepine, regardless of indication. For the non-benzodiazepine sleep aids, sites should only utilize one of the listed medications that are approved for this indication in their respective countries and the country specific prescribing information is to be used to determine the maximum allowable daily dose for the treatment of insomnia. Non-benzodiazepine sleep aids must not be administered within 12 hours prior to scheduled efficacy and safety assessments, including EPS scales. Investigators are encouraged to delay scale administration until 12 hours have elapsed, if at all possible. However, if delaying administration of efficacy and safety scales is not feasible, the scales should still be administered and the use of the sleep aid documented, including a notation of the drug name, dose, and time of administration in eSource.

| Table 4.1-3               | Oral Benzodiazepine Rescue Therapy During the Trial |                             |                                       |  |  |  |  |  |
|---------------------------|---|-----------------------------|---------------------------------------|--|--|--|--|--|
| Oral Benzodiazepine       | Maximum Allowable Dose (mg/day)                     |                             |                                       |  |  |  |  |  |
|                           | Screening   | Baseline to Week 2
Visit | After Week 2 Visit to
Week 6 Visit |  |  |  |  |  |
| Lorazepam a    | 3   | 3                           | 3                                     |  |  |  |  |  |
| Oxazepam a     | 45  | 45                          | 45                                    |  |  |  |  |  |
| Diazepam a,b   | 15  | 15                          | 15                                    |  |  |  |  |  |
| Clonazepam a,b | 1.5   | 1.5                         | 1.5                                   |  |  |  |  |  |

aBenzodiazepines must not be administered within 12 hours prior to scheduled efficacy and safety assessments, including EPS scales. Investigators are encouraged to delay scale administration until 12 hours have elapsed, if at all possible. However, if delaying administration of efficacy and safety

scales is not feasible, the scales should still be administered and the use of benzodiazepine documented, including a notation of the drug name, dose, and time of administration in eSource.

bIn countries or institutions where no short-acting benzodiazepines are commercially available, use of oral diazepam or oral clonazepam may be acceptable if prior authorization is obtained from the medical monitor.

Table 4.1-4 below provides a select list of CYP2D6 inhibitors and CYP3A4 inhibitors and inducers which are prohibited within 14 days of dosing and for the duration of the trial.

| Table 4.1-4         Selected CYP2D6 Inhibitors and CYP3A4 Inhibitors and
Inducers Prohibited During the Trial |                            |  |  |  |  |  |
|--|----------------------------|--|--|--|--|--|
| Inducers Pronibiled During the Trial   |                            |  |  |  |  |  |
| Selected CYI   | Selected CYP2D6 Inhibitors |  |  |  |  |  |
| Celecoxib  | Hydroxyzine                |  |  |  |  |  |
| Chloroquine  | Methadone                  |  |  |  |  |  |
| Chlorpheniramine   | Moclobemide                |  |  |  |  |  |
| Clemastine   | Paroxetine                 |  |  |  |  |  |
| Clomipramine   | Pyrilamine                 |  |  |  |  |  |
| Diphenhydramine  | Quinidine                  |  |  |  |  |  |
| Fluoxetine   | Terbinafine                |  |  |  |  |  |
| Halofantrine   | Tripelennamine             |  |  |  |  |  |
| Selected CYI   | P3A4 Inhibitors            |  |  |  |  |  |
| Amiodarone   | Fluvoxamine                |  |  |  |  |  |
| Amprenavir   | Indinavir                  |  |  |  |  |  |
| Aprepitant   | Itraconazole               |  |  |  |  |  |
| Chloramphenicol  | Ketoconazole               |  |  |  |  |  |
| Cimetidine   | Nefazodone                 |  |  |  |  |  |
| Clarithromycin   | Nelfinavir                 |  |  |  |  |  |
| Clotrimazole (if used orally)  | Quinupristin/Dalfopristin  |  |  |  |  |  |
| Delavirdine  | Ritonavir                  |  |  |  |  |  |
| Diltiazem  | Saquinavir                 |  |  |  |  |  |
| Erythromycin   | Troleandomycin             |  |  |  |  |  |
| Fluconazole  | Verapamil                  |  |  |  |  |  |
| Selected CY  | P3A4 Inducers              |  |  |  |  |  |
| Carbamazepine  | Phenytoin                  |  |  |  |  |  |
| Dexamethasone  | Primidone                  |  |  |  |  |  |
| Efavirenz  | Rifampin                   |  |  |  |  |  |
| Nevirapine   | St. John's Wort            |  |  |  |  |  |
| Oxcarbazepine  | Troglitazone               |  |  |  |  |  |
| Phenobarbital  |                            |  |  |  |  |  |

#### 4.2 Other Restrictions

#### 4.2.1 Restricted Therapies and Precautions

Any history of electroconvulsive therapy is exclusionary.

Use of intramuscular (IM) benzodiazepines is prohibited throughout the trial. Continual use of oral benzodiazepines is not permitted during the trial and subjects must discontinue routine benzodiazepine use, except those allowed per Table 4.1-3, for at least 2 weeks prior to the baseline visit. Subjects must not be on more than one benzodiazepine beyond screening. If a subject is receiving two benzodiazepines at screening (eg, lorazepam and oxazepam), attempts should be made to discontinue one of the benzodiazepines, if clinically warranted, to allow potential subjects to enter the trial. The second benzodiazepine should be tapered off over an appropriate amount of time within the 28-day screening period to prevent withdrawal effects prior to the first dose of IMP. Short-term use of specific oral benzodiazepines is allowed during the trial (including the prerandomization washout period) for the control of agitation or insomnia as shown in Table 4.1-3. Short-acting benzodiazepines (ie, lorazepam or oxazepam) are to be used whenever possible. In countries or institutions where no short-acting benzodiazepines are commercially available, use of oral diazepam or oral clonazepam may be acceptable if prior authorization is obtained from the medical monitor. The investigator should contact the medical monitor to discuss any subject who requires frequent use (defined as more days than not) of a benzodiazepine for agitation or insomnia beyond the first 2 weeks of the trial.

Non-benzodiazepine sleep aids (ie, zolpidem, zaleplon, zopiclone, and eszopiclone only) are permitted for the treatment of insomnia, but not on the same day as administration of a benzodiazepine, regardless of indication. For the non-benzodiazepine sleep aids, sites should only utilize one of the listed medications that are approved for this indication in their respective countries and the country-specific prescribing information is to be used to determine the maximum allowable daily dose for the treatment of insomnia.

Anticholinergics are permitted for the treatment of EPS up to a maximum of 4 mg/day benztropine or its equivalent and propranolol is permitted for akathisia or tremor up to a maximum of 60 mg/day. Subjects receiving a stable dose of propranolol for other conditions at entry into Trial 331-10-234 may remain on propranolol. Trial sites should only utilize medications that are approved for these indications in their respective countries.

Benzodiazepines, non-benzodiazepine sleep aids, anticholinergics, and propranolol must not be administered within 12 hours prior to scheduled efficacy and safety assessments, including EPS scales. Investigators are encouraged to delay scale administration until 12 hours have elapsed, if at all possible. However, if delaying administration of efficacy and safety scales is not feasible, the scales should still be administered and the use of the

medication documented, including a notation of the drug name, dose, and time of administration in eSource.

The subject's best medical interests should guide the investigator in the management of conditions that are pre-existing or that develop during the trial (intercurrent illness or AEs). The investigator should examine the acceptability of all concomitant medications not explicitly prohibited. In order to ensure that appropriate concomitant therapy is administered, it is essential that subjects be instructed not to take any medications (either self-administered non-prescription drugs or prescription therapy prescribed by another physician) without prior consultation with the investigator. All trial personnel should be familiar with the content of the IB for brexpiprazole in order to manage the subject's condition adequately and select appropriate concomitant medications, if needed.

# 4.2.2 Non-therapy Precautions and Restrictions

# 4.2.2.1 Precautions

Subjects should not undergo any elective medical procedure without prior consultation with the investigator. An elective procedure (eg. minor surgery, dental surgery, orthopedic surgery) that might require hospitalization or general anesthesia should be deferred until after the trial whenever clinically appropriate.

# 4.2.2.2 Restrictions

With the exception of inpatient group therapy, new-onset psychotherapy is prohibited during the trial. In other words, except for inpatient group therapy, subjects may only receive psychotherapy (eg, individual, group, marriage, or family therapy) if they have been participating in the therapy regularly (ie, weekly) for at least 6 weeks (42 days) prior to screening and commit to maintain their participation during the course of the trial at the current frequency or unless permission is obtained from the medical monitor.

Consumption of grapefruit, grapefruit products, Seville oranges, or Seville orange products within 72 hours prior to dosing and during the trial is prohibited. Subjects will be instructed to refrain from drinking alcoholic beverages or using illicit drugs during participation in the trial. The investigator may request a blood or urine drug screen at any time during the trial if there is a suspicion of illicit drug use.
# 5 Reporting of Adverse Events

#### 5.1 Definitions

An AE is defined as any untoward medical occurrence in a patient or clinical trial subject administered a medicinal product and which does not necessarily have a causal relationship with this treatment. AEs would not include information recorded as medical history at screening for preplanned procedures for which the underlying condition was known and no worsening occurred. An adverse reaction is any untoward and unintended response to an IMP related to any dose administered.

A suspected adverse reaction is any AE for which there is a reasonable possibility that the IMP caused the AE. For the purpose of IND safety reporting, "reasonable possibility" means there is evidence to suggest a causal relationship between the IMP and the AE. Suspected adverse reaction implies a lesser degree of certainty about causality.

An SAE includes any event that results in any of the following outcomes:

- Death
- Life-threatening; ie, the subject was, in the opinion of the investigator, at immediate risk of death from the event as it occurred. It does not include an event that, had it occurred in a more severe form, might have caused death.
- Persistent or significant incapacity/disability or substantial disruption of the ability to conduct normal life functions.
- Requires inpatient hospitalization or prolongs hospitalization.
  - Hospitalization itself should not be reported as an SAE; whenever possible the reason for the hospitalization should be reported.
  - Hospitalizations or prolonged hospitalizations for social admissions (ie, those required for reasons of convenience or other non-medical need) are not considered SAEs.
- Congenital anomaly/birth defect.
- Other medically significant events that, based upon appropriate medical judgment, may jeopardize the subject and may require medical or surgical intervention to prevent one of the outcomes listed above; eg, allergic bronchospasm requiring intensive treatment in an emergency room or home, blood dyscrasias or convulsions that do not result in hospitalization, or the development of drug dependency or drug abuse.

Nonserious adverse events are all AEs that do not meet the criteria for an SAE.

If a subject is experiencing an EPS, the specific EPS must be indicated on the AE screen in eSource. Examples of AEs that are considered EPS include, but are not limited to: generalized rigidity, hyperkinesia, bradykinesia, akinesia, dystonia, hypertonia, akathisia, tremor, flexed posture, involuntary muscle contractions, athetosis, and chorea. If a subject is experiencing 2 or more of these symptoms, whether or not treatment with an anticholinergic is required, this is considered as extrapyramidal syndrome and must be entered as "extrapyramidal syndrome" on the AE screen in eSource instead of the individual symptoms. Permitted treatments for EPS are described in Section 4.2.1.

Immediately Reportable Event (IRE):

- Any SAE.
- Any AE related to occupational exposure.
- Potential serious hepatotoxicity cases (any increase of AST or ALT ≥ 3 times the upper normal limit or screening value with an increase in total bilirubin ≥ 2 times the upper normal limit or screening value)
- Pregnancies are also defined as IREs. Although normal pregnancy is not an AE, it will mandate IMP discontinuation and must be reported on an IRE form to the sponsor. Pregnancy will only be documented on the AE screen in eSource if there is an abnormality or complication.

Clinical Laboratory Test Value Changes: It is the investigator's responsibility to review the results of all laboratory tests as they become available. This review will be documented by the investigator's dated signature on the laboratory report. For each abnormal laboratory test result, the investigator needs to ascertain if this is an abnormal (ie, clinically significant) change from baseline for that individual subject. This determination, however, does not necessarily need to be made the first time an abnormal value is observed. The investigator may repeat the laboratory test or request additional tests to verify the results of the original laboratory tests. If this laboratory value is considered medically relevant by the investigator (subject is symptomatic, requiring corrective treatment or further evaluation), or if the laboratory value leads to discontinuation, or fulfills a seriousness criterion, this is considered an AE.

Severity: Adverse events will be graded on a 3-point scale and reported as indicated in eSource. The intensity of an adverse experience is defined as follows:

- **1 = Mild:** Discomfort noticed, but no disruption to daily activity.
- **2** = **Moderate:** Discomfort sufficient to reduce or affect normal daily activity.
- **3 = Severe:** Inability to work or perform normal daily activity.

IMP Causality: Assessment of causal relationship of an AE to the use of the IMP is defined as follows:

| Related:     | There is a reasonable possibility of a temporal and causal relationship between the IMP and the AE. |
|--------------|---|
| Not Related: | There is no temporal or causal relationship between the IMP and the AE.                             |

# 5.2 Eliciting and Reporting Adverse Events

The investigator will periodically assess subjects for the occurrence of AEs. To avoid bias in eliciting AEs, subjects should be asked the non-leading question: "How have you felt since your last visit?" All AEs (serious and nonserious) reported by the subject must be recorded on the source documents and in eSource provided by the sponsor. The AE collection is to begin after a subject has signed the ICF.

Use medical terminology in AE reporting. Adverse events should be reported as a single unifying diagnosis whenever possible or, in the absence of a unifying diagnosis, as individual signs or symptoms. Exacerbation or disease progression should be reported as an AE only if there are unusual or severe clinical features that were not present, or experienced earlier, or not expected based on the course of the condition. A reported AE that undergoes a change in severity, seriousness, or toxicity should be reported as a new AE in eSource.

Note: Normal pregnancy is not an AE and should not be recorded as one in eSource; guidelines outlined in Section 5.5 should be followed for pregnancy reporting.

In addition, the sponsor must be notified immediately by telephone, fax, or e-mail of any IREs according to the procedure outlined below, in Section 5.3. Special attention should be paid to recording hospitalization and concomitant medications.

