# 3.7.6 Independent Data Monitoring Committee

A data monitoring committee (DMC) will provide oversight for safety monitoring. The details of the DMC structure and its roles and responsibilities will be documented in a DMC charter.

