# 7.4.3 Exploratory Endpoint Analysis

The change in the P-Q-LES-Q total score (ie, 14 items) will be summarized using an MMRM analysis with factors of treatment, trial site, visit, treatment by visit interaction, and baseline and baseline by visit interaction as covariates, with an unstructured variance covariance structure. All available data (OC dataset) will be applied in the model. Additionally, change from baseline in the overall score of P-Q-LES-Q will be summarized using the CMH row mean scores differ test controlling for trial site.

Hospitalization data will be summarized by 2 categories: hospitalization due to worsening schizophrenia and hospitalizations due to other causes.

Additional details for exploratory endpoint analysis are provided in the SAP.

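### Protocol 5.1 and 5.2 do not say which rule governs when an expected exacerbation of schizophrenia leads to admission, so SAE reporting and serious TEAE counts can depend on which section a site follows

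*Protocol*

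**What the plan says.** **Exacerbations (Protocol 5.2).** "Exacerbation or disease progression should be reported as an AE only if there are unusual or severe clinical features that were not present", and the sentence continues "or experienced earlier, or not expected based on the course of the condition". It has no clause for an exacerbation that is serious.

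**Seriousness (Protocol 5.1).** An SAE "includes any event that results in any of the following outcomes", and the list contains "Requires inpatient hospitalization or prolongs hospitalization". A sub-item adds: "Hospitalization itself should not be reported as an SAE; whenever possible the reason for the hospitalization should be reported". Social admissions are the only hospitalisations carved out. Every SAE is an immediately reportable event (IRE).

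**Laboratory values (Protocol 5.1).** If a value "fulfills a seriousness criterion, this is considered an AE". Here the protocol does say that seriousness settles whether something is an AE.

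**Where the data go.** Protocol 7.6.1 tabulates serious TEAEs, and SAP 9.2 defines a TEAE as a kind of AE. Protocol 5.2 asks sites to take particular care in recording hospitalisations. Protocol 7.4.3 summarises them in two categories, "hospitalization due to worsening schizophrenia and hospitalizations due to other causes", as an exploratory analysis. Protocol 3.7.6 says "A data monitoring committee (DMC) will provide oversight for safety monitoring" and leaves the details to a charter that is not among the documents.

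**The concern.** The trial withdraws prior antipsychotics from adolescents with a PANSS Total Score of at least 80. It then randomises a third of them to six weeks of placebo, with outpatient conduct planned. Worsening psychosis is therefore a foreseeable harm, and admission is its most visible form. If two sites can see the same admission and one files an SAE while the other files nothing, the serious TEAE rates partly measure site habit. With an estimated 120 sites and small expected counts, a few discordant cases could change the table. The affected event class is also one on which the arms should differ if treatment works, so under-reporting need not cancel between arms.

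**Working it through.** No figure in the plan is at issue, so there is none to reproduce. The check is a comparison of text, followed by an illustration of size.

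**Step 1: one case under both rules.** Take a subject admitted with a picture that matches an earlier episode and that the investigator regards as expected.

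| Question | Following 5.2 | Following 5.1 |
|---|---|---|
| Is the exacerbation reported? | No: its features were experienced before and are expected | Yes: it is an event that required admission |
| Does the admission change that? | No clause says so | Yes: it is a listed seriousness outcome |
| What is filed? | Possibly nothing, since the reason for admission is not an AE | SAE and IRE, naming the exacerbation as the reason |

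Both sites can point to protocol text. No sentence ranks the two sections.

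**Step 2: is the gap deliberate?** The laboratory clause in 5.1 shows that the drafters knew how to write a seriousness override. The exacerbation rule has no counterpart, and nothing explains the difference.

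**Step 3: the effect on the tables.** The TEAE definition in SAP 9.2 starts from an AE. An exacerbation never entered as an AE cannot become a serious TEAE. It can still appear in the separate hospitalisation summary of Protocol 7.4.3.

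**Step 4: size.** The documents give no admission rate, so a range is assumed: 3%, 5% and 10% of 105 placebo subjects admitted for worsening.

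- 105 × 0.03 = 3.15
- 105 × 0.05 = 5.25
- 105 × 0.10 = 10.5

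That is about 3 to 11 subjects. It is an upper bound at each rate because it counts every such admission as discordant. Admissions with new, unusual or unexpected features are AEs under both sections.

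**Step 5: distribution over arms.** Suppose admission occurs when PANSS change crosses a threshold, with SD 19 (Protocol 7.1). For a placebo rate p, the active-arm rate is Φ(z(p) − δ/19). Take δ = 7.4 for brexpiprazole (the planning effect). For aripiprazole take either 7.4 (rounded from the 7.40 observed at 30 mg) or 5.46 (observed at 10 mg), both from the earlier adolescent trial in the synopsis. With 1:1:1 allocation the placebo share is p / (p + brexpiprazole rate + aripiprazole rate).

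Example, p = 0.05, aripiprazole δ = 5.46: the active rates are 0.0210 and 0.0267, and 0.05 / (0.05 + 0.0210 + 0.0267) = 0.51.

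| Placebo rate | Share, 7.4 in both arms | Share, 7.4 and 5.46 | Share, no drug effect |
|---|---|---|---|
| 2% | 58% | 54% | 33% |
| 5% | 54% | 51% | 33% |
| 10% | 51% | 49% | 33% |
| 15% | 49% | 47% | 33% |
| 20% | 48% | 46% | 33% |

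Under these assumptions placebo is the largest single contributor if the drugs work. Whether it contributes a majority depends on the assumed rate.

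**The case against.** The best reply is that 5.1 already covers these admissions. It speaks of any event, not of events already classed as AEs. It excludes only social admissions, and by telling sites to report the reason it presumes that the reason is reportable. The IRE form is separate from the AE screen (Protocol 5.3), and normal pregnancy shows that something other than an AE can require one. The 5.2 rule also admits severe features, and an admission from a trial planned for outpatients may well qualify. Finally, hospitalisations are recorded, eSource data populate the trial database under remote monitoring (Protocol 9.2), and withdrawals are notified promptly (Protocol 3.8.3.3).

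Much of this stands. Non-reporting is one permitted reading and not the necessary one, and a careful site could well report. It does not remove the conflict. The severity wording in 5.2 is tied to features not present or experienced earlier, so a severe repeat of a severe episode can fail the test. Recording an admission in eSource does not make it an SAE or start an immediate report.

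Three stronger inferences are tempting, and the documents do not support them:

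- *The DMC would not see these admissions.* What it receives is set in a charter that is not provided. The text supports only that they may not arrive through the SAE route.
- *Most unreported admissions would be on placebo.* No admission rates are given, and the illustrative share is 46% to 58%, or 33% with no drug effect.
- *Coding placebo withdrawals as AE or lack of efficacy would shift the SAP 8.1.2 sensitivity scenarios.* The delta is added only to brexpiprazole dropouts, and placebo-based imputation fills placebo values from placebo data in any case.

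**Conclusion.** The conflict between 5.1 and 5.2 is real and unresolved, and it is more than a missing detail: a site obeying the stated rule in 5.2 can omit an event that 5.1 makes serious. Serious TEAE counts, and possibly immediate reporting, could then vary with the section a site followed. Under-reporting could understate serious harm, more so on placebo if the drugs work.

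The size is modest and uncertain: at most about 3 to 11 of 105 placebo subjects, resting wholly on the assumed 3% to 10% admission rate. The conflict itself does not depend on that rate. The primary efficacy analysis is not in question. The point should be corrected because the change is cheap and concerns safety reporting in adolescents.

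**What to change.** 1. **Reconcile the sections.** Add one sentence to Protocol 5.2, for example: *Any worsening of schizophrenia that meets a seriousness criterion in Section 5.1, including inpatient admission, is reported as an SAE and an IRE, whether or not it was expected or resembles earlier episodes.* This gives exacerbations the override that laboratory values already have.
2. **Reconcile the data.** Before database lock, compare the hospitalisation records behind Protocol 7.4.3 with the SAE reports and query every admission for worsening schizophrenia that has no matching report.

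The cost is a one-sentence amendment, brief site retraining, somewhat more SAE reports and one additional data-management check. No dose, rescue or stopping rule changes.
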